4.1.2 Conditional discontinuation of study treatment in Maximum Responder Participants

In some participants the study treatment might no longer be required because of disease modification by ligelizumab and/or by simply outgrowing the allergy (Savage, Johns 2015). Therefore, conditional discontinuation of study drug is started in all participants whose responder status is MR (maximum responder) as shown in Figure 4-2 (for the participants from

Study CQGE031G12301 who transition at EOFu of the core study and Figure 4-3 for the participants from other study(ies) who transition at End of Treatment (EoT) of the core study).

For the participants who meet the definition of Maximum Responder (MR, see below), the interruption of the study drug will be commenced and participants will continue off-treatment, unless the sensitivity to the food returns based on the OFC (no longer MR).

The detailed process of the treatment for the MR participants is summarized in the Section 4.1.2.1.

This conditional discontinuation of study drug will be controlled by Interactive Response Technology (IRT) which informs the investigator about the treatment/off-treatment in each participant based on the outcome from DBPCFC (at EoT of a core study) / OL-OFC (in the extension study).

Table 4-1 Maximum Responder during the DBPCFC/OL-OFC

Responder status	Dose of allergen (food)
Maximum Responder (MR)	Maximum Tolerated Dose (MTD) of CCI ■ Participant WITHOUT Dose Limiting Symptom (DLS) at any dose including the maximum dose, CCI
DBPCFC will be conducted at the OL-OFC will be conducted during	e end of treatment period of the core study g the extension study

4.1.2.1 Detailed process for study treatment and conditional discontinuation of study treatment in MR participants

The conditional discontinuation of study treatment can only be performed once. In other words, if following study treatment interruption, the MR responder status is not confirmed at the next OFC, the study treatment should be restarted and continue until the end of treatment (Week 156), (unless participants are permanently discontinued from study treatment earlier see Section 7.1).

The processes of study treatment and conditional discontinuation of study treatment in the first, second and third year of the extension study are summarized below.

The participants who transition from Study CQGE031G12301 (Figure 4-2)

First year

- Participants who meet the definition of MR by DBPCFC at EoT of the core study and transition from the core study at EOFu will perform an OL-OFC at Screening/Day 1:
 - If the participants still meet the definition of MR by OL-OFC on Day 1, the off-treatment period will be continued until Week 52.
 - If the participants are no longer MR by OL-OFC on Day 1, the study treatment will be started (same dose as in the core study) after at least 24 h from completion of the OL-OFC on Day 1. If participants become MR again at a later timepoint, no interruption of treatment is commenced. The study treatment will continue until the EoT of the extension study (Week 156).
- NOTE: The Investigator is able to check the level of desensitization by SPT at Week 24 (scheduled time point) and can decide to conduct ad hoc OL-OFC in case of positive (or

shift from prior assessment) SPT. The same (SPT followed by OL-OFC) is allowed in case of suspected allergic event during the off-treatment period. The results of the ad hoc OL-OFC may lead to the resumption of study treatment (same dose as in the core study) after at least 24 h from completion of the OL-OFC and treatment will continue until the EoT of the extension study (Week 156).

• Participants who did not meet the definition of MR by DBPCFC at EoT of the core study and transition from the core study at EOFu will not perform an OL-OFC at Screening/Day 1. Study treatment will be started (same dose as in the core study) until week 52.

Second year:

[figure not shown]
- For participants who have been off-treatment in the first year until Week 52 (i.e., MR participants since Day 1):
 - 1. If the participants still meet the definition of MR by OL-OFC at Week 52, the off-treatment period will continue up to Week 104 of the extension study.
 - 2. If the participants are no longer MR by OL-OFC at Week 52, the study treatment will be re-started (same dose as in the core study) after at least 24 h from completion of the OL-OFC. If the participants become MR again at a later timepoint, no interruption of treatment is commenced. The study treatment will continue until the EoT of the extension study (Week 156).
- NOTE: The Investigator is able to check the level of desensitization by SPT at Week 76 (scheduled time point) and can decide to conduct an ad hoc OL-OFC in case of positive (or shift from prior assessment) SPT. The same (SPT followed by OL-OFC) is allowed in case of a suspected allergic event during the off-treatment period. The results of the ad hoc OL-OFC may lead to the resumption of study treatment (at the same dose as in the core study) after at least 24 h from completion of the OL-OFC, and treatment will continue until the EoT of the extension study (Week 156).
- For participants who have received the study treatment in the first year until Week 52 (i.e., participants who did not have OL-OFC at Screening/Day 1):
 - 1. If the participants meet the definition of MR by OL-OFC at Week 52, the interruption of study treatment (off-treatment) will be initiated.
 - If the participants still meet the definition of MR by OL-OFC after 16 weeks of study treatment interruption (at Week 68), the interruption (off-treatment) period will be extended up to Week 104.
 - If the participants are no longer MR by OL-OFC after 16 weeks of study treatment interruption (at Week 68), the study treatment will be re-started (same dose as in previous year) after at least 24 h from completion of the OL-OFC. If the participants become MR again at a later timepoint, no interruption of treatment is commenced. The study treatment will continue until the EoT of the extension study (Week 156).
- NOTE: The investigator is able to check the level of desensitization by SPT at an unscheduled time point prior to Week 104, and the results of the ad hoc OL-OFC may lead to the resumption of study treatment (same dose as taken previously) after at least 24 h from completion of the OL-OFC and treatment will continue until the EoT of the extension study (Week 156).

• If the participants do not meet the definition of MR by OL-OFC at Week 52, the study treatment will be continued (same dose as in the previous year) until Week 104.

Third year:

- For participants who have been off-treatment in the second year until Week 104:
 - 1. If the participants meet the definition of MR by OL-OFC at Week 104, the off-treatment period will continue up to Week 156.
 - 2. If the participants are no longer MR by OL-OFC at Week 104, the study treatment will be re-started (same dose as in previous year) after at least 24 h from completion of the OL-OFC. The study treatment will continue until the EoT of the extension study (Week 156).
- NOTE: The Investigator is able to check the level of desensitization by SPT at Week 128 (scheduled time point) and can decide to conduct an ad hoc OL-OFC in case of positive (or shift from prior assessment) SPT. The same (SPT followed by OL-OFC) is allowed in case of suspected allergic event during the off-treatment period. The results of the ad hoc OL-OFC may lead to the resumption of study treatment (same dose as in core or previous year) after at least 24 h from completion of the OL-OFC, and treatment will continue until the EoT of the extension study (Week 156).
- For participants who have received the study treatment continuously until Week 104:
 - If the participants meet the definition of MR by OL-OFC at Week 104, the off-treatment period will be initiated (unless the participants met MR earlier and already had treatment interruption, in which case treatment continues with the same dose).
 - 1. If the participants still meet the definition of MR by OL-OFC after 16 weeks of study treatment interruption (at Week 120), the off-treatment period will be extended up to Week 156.
 - 2. If the participants are no longer MR by OL-OFC after 16 weeks of study treatment interruption (at Week 120), the study treatment will be re-started (same dose as in previous year) after at least 24 h from completion of the OL-OFC. The study treatment will continue until the EoT of the extension study (Week 156).
- NOTE: The investigator is able to check the level of desensitization by SPT at an unscheduled time point prior to Week 104, and the results of the ad hoc OL-OFC may lead to the resumption of study treatment (same dose as previously) after at least 24 h from completion of the OL-OFC, and treatment will continue until the EoT of the extension study (Week 156).
 - If the participants do not meet the definition of MR by OL-OFC at Week 104, the study treatment will be continued (same dose as in previous year) until Week 156.

Figure 4-2 Conditional discontinuation for the MR participants who transition from Study CQGE031G12301

The participants who transition from other study(ies) (Figure 4-3)

First year:

No conditional discontinuation is allowed even if the participants meet the definition of MR by DBPCFC at EoT of the core study. The first visit of the extension study (Screening/Day 1) will be scheduled 4 weeks after EoT of the core study, and the study treatment will be continued (same dose as in the core study) for the first year of extension study.

Second year:

[figure not shown]
- If the participants meet the definition of MR by OL-OFC at Week 52 of the extension study, the interruption of study treatment (off-treatment) will be initiated:
 - 1. If the participants still meet the definition of MR by OL-OFC after 16 weeks of study treatment interruption (at Week 68), the interruption (off-treatment period) will be extended up to Week 104.
 - 2. If the participants are no longer MR by OL-OFC after 16 weeks of interruption (at Week 68), the study treatment will be re-started (same dose as in previous year) after at least 24 h from completion of the OL-OFC. If the participants become MR again at a later timepoint, no interruption is commenced. The study treatment will continue until the EoT of the extension study (Week 156).
- NOTE: The Investigator is able to check the level of desensitization by SPT at an unscheduled time point prior to Week 104 and can decide to conduct ad hoc OL-OFC in case of positive (or shift from prior assessment) SPT. The same (SPT followed by OL-OFC) is allowed in case of suspected allergic event during the off-treatment period. The results of the ad hoc OL-OFC may lead to the resumption of study treatment (same dose as in the core

- study) after at least 24 h from completion of the OL-OFC, and treatment will continue until the EoT of the extension study (Week 156).
- If the participants do not meet the definition of MR by OL-OFC at Week 52, the study treatment will be continued (same dose as in previous year) until Week 104.

Third year:

- For participants who have been off-treatment in the second year until Week 104
 - 1. If the participants meet the definition of MR by OL-OFC at Week 104, the off-treatment period will continue up to Week 156.
 - 2. If the participants are no longer MR by OL-OFC at Week 104, the study treatment will be re-started (same dose as in previous year) after at least 24 h from completion of the OL-OFC. The study treatment will continue until the EoT of the extension study (Week 156).
- NOTE: The Investigator is able to check the level of desensitization by SPT at an unscheduled time point prior to Week 156 and can decide to conduct ad hoc OL-OFC in case of positive (or shift from prior assessment) SPT. The same (SPT followed by OL-OFC) is allowed in case of suspected allergic event during the off-treatment period. The results of the ad hoc OL-OFC may lead to the resumption of study treatment (same dose as in previous year) after at least 24 h from completion of the OL-OFC. The study treatment will continue until the EoT of the extension study (Week 156).
- For participants who have received the study treatment continuously until Week 104
 - If the participants meet the definition of MR by OL-OFC at Week 104, the interruption of study treatment (off-treatment period) will be initiated.
 - 1. If the participants still meet the definition of MR by OL-OFC after 16 weeks of the study treatment interruption (at Week 120), the interruption (off-treatment period) will be extended up to Week 156.
 - 2. If the participants are no longer MR by OL-OFC after 16 weeks of interruption (at Week 120), the study treatment will be re-started (same dose as in previous year) after at least 24 h from completion of the OL-OFC. The study treatment will continue until the EoT of the extension study (Week 156).
- NOTE: The Investigator is able to check the level of desensitization by SPT at an unscheduled time point prior to Week 156 and can decide to conduct ad hoc OL-OFC in case of positive (or shift from prior assessment) SPT. The same (SPT followed by OL-OFC) is allowed in case of suspected allergic event during the extended washout. The results of the ad hoc OL-OFC may lead to the resumption of study treatment (same dose as in previous year) after at least 24 h from completion of the OL-OFC. The study treatment will continue until the EoT of the extension study (Week 156).
 - If the participants do not meet the definition of MR by OL-OFC at Week 104, the study treatment will be continued (same dose as in previous year) until Week 156.

Figure 4-3 Conditional discontinuation for the MR participants who transition from other studies

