⁵ Depending on the responder status, participants may not receive study treatment at every visit. If participant is a Maximum Responder, they will conditionally discontinue treatment until the next scheduled OFC for Maximum Responders.

Period	Follow-up	ollow-up							
Visit Name	WK 160	WK 164	WK 168	EoS/PSD					
Weeks	160	164	168	172					
Days	1120	1148	1176	1204					

⁶ For MR participants defined by previous OFC which have changed responder status (no longer MR), the study treatment should be administered at least 24-hours after OFC.

⁷ Only for participants transitioning from Study CQGE031G12301 who were MR at DBPCFC at EoT

⁸ Ad hoc OL-OFC visits based on the SPT at Weeks 24, 76, 128 (scheduled time points) or prior to Week 104 and/or 156 (unscheduled time points) to allow the Investigator to check the level of desensitization. Investigator may conduct ad hoc OL-OFC in case of positive (or shift from prior assessment) SPT. The same (SPT followed by OL-OFC) is allowed in case of suspected allergic event during the extended wash out. The results of the ad hoc OL-OFC might lead to the resumption of study treatment (same dose as in the core study or in the previous year) for patients currently undergoing conditional discontinuation.

⁹ Ad hoc OL-OFC visit for patients who meet the definition of MR at weeks 52 and 104 and have completed a 16-week wash-out period to determine if the study treatment should be restarted.

2 Introduction

In the last years, food allergy is rising worldwide affecting people of all ages and nations, with an increase in prevalence and costs associated with the disease making it an emerging population health priority (Gupta et al 2013, Gupta et al 2019, Warren et al 2020). Recent data demonstrate that between one-third and one-half of food allergy patients, including adults, are likely to be allergic to more than one food (Gupta et al 2019). Among food types, peanut, milk and egg represent a high prevalence of food allergens and the ingestion of even small quantities of the these allergens may lead to a severe and potentially life-threatening allergic reaction (Savage et al 2003, Fair Health White Paper 2017).

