6.2.3 Instruction for prescribing and taking study treatment

The independent study treatment administrator or unblinded pharmacist will administer the study treatment to the participant during the study visit without engaging in any unnecessary interactions that may have the potential to un-blind the participant or any of the study site personnel.

The subcutaneous injections can be administered in the deltoid region on the upper right and/or left arm, the lower stomach area (but not the area 5 cm around the belly button) and/or into the front of the right and/or left thigh, or the abdomen as preferred by the participant and/or site. Do not inject into skin that is tender, bruised, red, scaly, hard or into areas with scars or stretch marks. Each injection must be administered at a different site (e.g., right arm and left thigh). The guidelines for the preparation and administration of study treatment are described in the pharmacy manual (provided separately).

Participants who join the study after the follow-up period of the core study will remain on site for observation for a period of **2 h post-dose** for the first three drug administration visits, this equates to week 0, 4 and 8. Thereafter a 30 minute wait will suffice. Participants who join the extension study from continuous treatment will only require a 30 minute wait at the site. The 2-hour observation period for the first three drug administrations must be observed in all instances where study treatment is reintroduced after a washout/interruption period (e.g., restart of the

study treatment after the conditional discontinuation of study treatment because of no longer MR).

At Week 52, 104, and 156 there must be a minimum of 1 hour between administration of study treatment and performing the OFC (Section 8.3.1). Study treatment must be given before the OFC.

In case the study treatment should be started based on the responder driven approach (Previous MR is no longer MR after off-treatment, Section 4.1.2), the time interval between OFC and restart of study treatment must be a minimum of 24 h.

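### Protocol 4.1.2.1, third year: the note on unscheduled checks for CQGE031G12301 participants who stop drug at Week 104 names a window that closes before that interruption begins

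*Protocol*

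**What the plan says.** Protocol 4.1.2.1 sets the interruption rules year by year, separately for participants from CQGE031G12301 and from other studies. Protocol 2.1 says that the present protocol admits only the former.

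The third-year text for CQGE031G12301 contains a branch introduced by "For participants who have received the study treatment continuously until Week 104". Its rule is: "If the participants meet the definition of MR by OL-OFC at Week 104, the off-treatment period will be initiated". Those who remain Maximum Responders (MR) continue off drug: "after 16 weeks of study treatment interruption (at Week 120), the off-treatment period will be extended up to Week 156". The note directly beneath lets the investigator do a skin prick test (SPT) at an unscheduled time "prior to Week 104, and the results of the ad hoc OL-OFC may lead to the resumption of study treatment (same dose as previously".

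Four other places bear on the same matter:

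- The second-year note for CQGE031G12301 participants whose interruption starts at Week 52 shares the wording "at an unscheduled time point prior to Week 104, and the results of the ad hoc OL-OFC may lead to the resumption".
- The third-year note for participants from other studies, whose interruption also starts at Week 104, has "SPT at an unscheduled time point prior to Week 156 and can decide to conduct ad hoc OL-OFC".
- Footnote 8 of Table 1-4 (Protocol 1.3) allows ad hoc open-label challenges (OL-OFC) at Weeks 24, 76 and 128, "or prior to Week 104 and/or 156 (unscheduled time points) to allow the Investigator to check the level of desensitization". It also allows SPT followed by OL-OFC when an allergic event is suspected during the wash-out.
- Protocol 2.3, on conditional discontinuation, allows restart once an interruption has begun, on clinical or other findings and after an optional OL-OFC. It names no week.

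**The concern.** The note is there to say how loss of tolerance can be picked up, and treatment resumed, between scheduled challenges. As worded, it does this for a period in which the participants concerned are still on drug.

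The rule matters because Protocol 6.5.4 makes restart depend on a food challenge showing that the participant is no longer MR. Between scheduled challenges, the ad hoc OL-OFC is therefore the way back to treatment. Protocol 4.1.2 puts on- and off-treatment status under the response technology system, driven by challenge outcomes, and Protocol 8 rules out waivers and exemptions. A site that works from the detailed rule alone finds no usable unscheduled window after Week 104, while a site that works from the schedule footnote finds one. The affected branch belongs to the only population now admitted.

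There is an analytical side as well. Protocol 9.3.2 plans separate safety tables for participants who restart after a mandated interruption. If sites read the window differently, the timing of those restarts would depend partly on which text they followed.

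**Working it through.** The check is calendar arithmetic and interval overlap.

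**Start of the interruption.** MR status is established by the Week 104 OL-OFC. Protocol 6.2.3 puts dosing first on that day: "At Week 52, 104, and 156 there must be a minimum of 1 hour between administration of study treatment and performing the OFC". Off-drug time in this branch therefore cannot begin before the Week 104 visit.

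**Reproducing the plan's own figure.** 104 + 16 = 120, which is the stated week of the follow-up challenge. In the days of Table 1-4: 104 × 7 = 728, 120 × 7 = 840 and 156 × 7 = 1092.

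**Length of the interruption.** From 120 − 104 = 16 weeks up to 156 − 104 = 52 weeks.

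**Overlap of each unscheduled-check note with the interruption it accompanies (4.1.2.1):**

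| Cohort and year | Off-treatment period | Note's window | Overlap |
|---|---|---|---|
| CQGE031G12301, year 2, interrupted at Week 52 | Weeks 52–104 | before Week 104 | up to 104 − 52 = 52 weeks |
| CQGE031G12301, year 3, interrupted at Week 104 | Weeks 104–156 | before Week 104 | 0 weeks |
| Other studies, year 2, interrupted at Week 52 | Weeks 52–104 | before Week 104 | up to 52 weeks |
| Other studies, year 3, off drug since year 2 | continues Weeks 104–156 | before Week 156 | up to 156 − 104 = 52 weeks |
| Other studies, year 3, interrupted at Week 104 | Weeks 104–156 | before Week 156 | up to 52 weeks |

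Only the second row has no overlap. The note cannot be meant for participants interrupted at Week 52, because the second-year text already gives them their own, nearly identical note.

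**Triggers.** Section 4.1.2.1 has eight notes on checks while off treatment: five for CQGE031G12301 (Weeks 24, 76 and 128, and two unscheduled) and three for other studies. Six carry a suspected-allergic-event clause. The two without it are the unscheduled second-year and third-year notes for CQGE031G12301. Footnote 8 carries the clause without naming a cohort or week.

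**Checks available after Week 104 when the whole protocol is read.** OL-OFC is planned at Weeks 120 and 156. Table 1-4 also has an SPT and an ad hoc OL-OFC entry at Week 128, with no cohort restriction on the SPT. Counting from the Week 104 challenge, the gaps are 120 − 104 = 16, 128 − 120 = 8 and 156 − 128 = 28 weeks. Footnote 8 and Protocol 2.3 add unscheduled checks.

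**The case against.** The best defence is that the note is permissive and does not stand alone. It says what the investigator may do and forbids nothing at other times. Footnote 8 extends to Week 156 and covers suspected allergic events. Protocol 2.3 and 6.5.4 allow restart with no week limit. Protocol 1.3 provides phone contact every 4 weeks during an interruption, and Table 1-4 places an SPT at Week 128. On this view the note is a carry-over from the second-year text, where Week 104 fits.

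Most of this stands, and it rules out three stronger readings that a reader might infer:

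- *Participants off drug after Week 104 have no stated route to an unscheduled check.* That is true only of this note read in isolation.
- *They go 52 weeks with nothing but the Week 120 challenge.* This overlooks the Week 128 entries in Table 1-4. The Week 128 note in 4.1.2.1 is attached to a different group, but the table entries are not.
- *The note, the other-studies note and footnote 8 all contradict one another for the admitted population.* The other-studies note governs a cohort not yet admitted, so it serves only as a comparison. Footnote 8 contains the note's window and goes beyond it.

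The omitted allergic-event clause is not peculiar to the third-year note either, since the second-year note lacks it too.

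The defence does not remove the mismatch inside the branch. A note about resuming treatment still points to a time when treatment has not stopped, and a carry-over error, if that is what it is, remains an error in current operating text.

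**Conclusion.** The inconsistency is real and follows from the text alone: the stated window and the interruption it accompanies have no week in common. The note conflicts with its own branch and is narrower than footnote 8 and Protocol 2.3. It concerns the detection of returning sensitivity off drug in the admitted population, so it deserves correction. Its size is bounded because other provisions cover the period after Week 104.

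The conclusion assumes that the note belongs to the branch directly above it, as its position and the presence of a separate second-year note indicate. The missing figure for this cohort (Figure 4-2) would not alter the words. That the text was carried over from year two is a plausible inference which the documents do not confirm.

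Practical impact may be limited. The SAP introduction reports early termination for strategic reasons, and neither document shows whether anyone entered a Week 104 interruption.

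**What to change.** The sponsor should reconcile the third-year CQGE031G12301 note in Protocol 4.1.2.1 with Table 1-4 footnote 8, the restart statement in Protocol 2.3 and the third-year notes for other studies. The stated window should agree across these places and fall within the off-treatment period it describes. The same pass should align the triggers in the second-year and third-year unscheduled notes for CQGE031G12301 with those in footnote 8 and the remaining notes. Which window and triggers apply is a clinical decision for the sponsor and is not proposed here.

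The cost is a wording correction by protocol amendment, with no change to sample size or planned analyses. If no further amendment will be issued because of the termination, the correction should be made before the text is reused. The study report could also state whether any participant entered a Week 104 interruption and, if so, which rule the sites followed.
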